After completion of baseline questionnaires (MPQ-SF, DSI, CATS) the Brief CBT Intervention will be viewed by the subject. Upon completion of the presentation, the CATS questionnaire will be administered again. The subject will receive a packet containing "The Power of the Mind," they will be asked to read this information and complete the exercise at the end of the packet. The study staff will call the subject one week after the initial meeting and ask if they have read the packet and will also have the subject to complete the CATS questionnaire again. A postage paid, addressed envelope will be provided for the subject to return the questionnaires to the study team. The questionnaires will be de-identified and only contain subject initials and study identification number.

At Home Diary Assessments

The subject will be given a notebook with paper questionnaires and instructions on how to complete the questionnaires per the schedule below. All participants will complete the assessments in a sequence using one of several methods:

- A. Inpatient evaluation (surgery to discharge): Nursing staff will inquire about the patients pain levels using standard of care methods and assessment tools (e.g., numerical rating scale 0 – 10).
- B. Ecological Momentary assessment (discharge to day 14): The subject will complete the questionnaires in the morning and in the evening.
- C. Once daily (day 15 to day 28): The patient is instructed to complete a diary entry at the end of their day, just prior to going to sleep.
- D. Once weekly (day 29 to day 85): The patient will be called at their home and participate in a brief interview.
- E. Once monthly (day 86 to day 168): The patient will be called at their home and participate in a brief interview once each month.

Each of the assessments will only require about 5 to 10 minutes to complete. At each of the at home assessments the McGill Pain Questionnaire-SF will be administered.

In addition, information from the postoperative care from the orthopedic surgery division will be recorded, including range of joint motion and functional limitations, if any, at the times of routine postoperative clinic visits.

Table 1. A summary of the data collection procedures for the observational study

| Assessment Type | Time (Days) | Questionnaires | Joint Sensory Testing | Thermal Pain Testing | DNIC Protocol | Diary type |

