|-----------------|-------------|----------------|-----------------------|----------------------|---------------|---------------------------------|
| Visit 1 | -14 to 0 | X | X | X | X | NA |
| Post-op | 0 to 3 | | | | | NA |
| Home | 4 to 14 | | | | | Ecological Momentary Assessment |
| Home | 15 to 28 | | | | | Once-daily |
| Home | 29 to 85 | | | | | Weekly |
| Home | 86 to 168 | | | | | Monthly |

Outcome Measure(s)

The primary outcome measure for this study is self-reported pain intensity. To obtain estimates of pain intensity, we will use the McGill Pain Questionnaire - Short Form (MPQ). This instrument has been extensively used to assess pain in a wide variety of settings, and is uniquely suited to our present study in that the items can be completed while in a post-operative setting as well as a daily diary setting.

Analytical Plan

The proposed pilot study aims at identifying effect size estimates and indicators of feasibility. As such, the analytical plan is primarily descriptive in nature. Careful attention will be given to missing data due to any reason, participant withdrawal, and evidence of corrupted or invalid assessments. These threats to data collection will be itemized and descriptive statistics will be used to summarize the rates and expected proportions (with 95% confidence intervals) of measurements that may be lost due to any reason.

To estimate individual variability in the trajectory of pain over time (i.e., healing and diminishing pain reports), and predictors of that trajectory, hierarchical linear modeling (Raudenbush & Bryk, 2002) will be used. The application of HLM in individual change data is well suited for the examination of post surgery pain. Briefly, change trajectories are created for each participant. Because of the nature of the expected change, the trajectories will be modeled using an intercept, slope, and quadratic term. The intercept is coded to represent the baseline level of the pain score (day of surgery). The slope estimates the linear change over time and represents the increase or decrease in the variable. Finally, the quadratic term estimates the acceleration or deceleration over time and reflects changes in the rate of change in pain reporting.

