To assess our specific hypotheses, we will first evaluate the appropriateness of a model that consisted of only intercept (starting value), time, and time-squared as first-level predictors. This first level model describes individual trajectories (change) across time. This model will be evaluated for fit, redundancy, and variability in the parameters and will be reduced to a linear change model if conditions indicate. When a suitable first-level model is developed, and if there is significant variation across participants in either the intercept or change parameters, a second level model will be specified. The second level model will examine the impact of the questionnaires and baseline sensory testing on the trajectories (i.e., linear and quadratic components of the first level model). In all cases, the model coefficients and their standard errors will be of primary interest to inform out later, definitive study.

Risks

Taking part in this research study may involve subject's providing information that they consider confidential or private. Efforts, such as coding research records, keeping research records secure and allowing only authorized people to have access to research records, will be made to keep research related information safe.

Human Subjects Protection

Subject Recruitment Methods

Patients scheduled for unicompartmental knee, total knee replacement, or total hip replacement surgery at WFUHS will be contacted by telephone by our research nurse at least 2 days before surgery. All adult patients scheduled for surgery within the inclusion criteria discussed above will be considered as eligible, regardless of sex, race, or ethnicity. Privacy will be protected by safekeeping and then destruction of surgical posting lists obtained from the Division of Orthopedic Surgery and by the maintenance of all records on password protected computers.

Patient name, age, telephone number, surgical indication, date and procedure scheduled for major joint surgery will be collected to identify and contact potential participants.

This information will be kept on print out in a locked location or on a WFUHS password protected computer. Print out will be shredded and file containing the name will be deleted within 24 hr of declining to participate.

Informed Consent

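### The trajectory model names no time form that can level off, and its intercept sits at the day of surgery, where no MPQ-SF is scheduled

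*Combined protocol and SAP*

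**What the plan says.** The primary outcome is pain intensity on the MPQ-SF (Outcome Measure(s)). The Analytical Plan says "the trajectories will be modeled using an intercept, slope, and quadratic term", and fixes the origin: "The intercept is coded to represent the baseline level of the pain score (day of surgery". The change it expects is "healing and diminishing pain reports".

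On model checking it says "This model will be evaluated for fit, redundancy, and variability in the parameters" and that the model "will be reduced to a linear change model if conditions indicate". No other time form is named and no fit criterion is given. Second-level predictors are then examined on the trajectories, with a parenthesis that mentions only the linear and quadratic parts. The plan treats the resulting coefficients and standard errors as its main product for the definitive study.

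On measurement, At Home Diary Assessments, item A, covers surgery to discharge: "Nursing staff will inquire about the patients pain levels using standard of care methods and assessment tools", with a 0-10 rating as the example. The same section ties the outcome instrument to home: "At each of the at home assessments the McGill Pain Questionnaire-SF will be administered". Table 1 marks no questionnaire and no diary for days 0 to 3 and starts the home diary at day 4. The one earlier MPQ-SF is pre-operative. Outcome Measure(s) adds that "the items can be completed while in a post-operative setting as well as a daily diary setting", which describes the instrument but schedules nothing.

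**The concern.** There are two mismatches.

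First, the intercept is defined at a time when the outcome is not scheduled to be measured. The linear coefficient in a quadratic is the slope at the origin, so it inherits the same problem.

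Second, healing pain may fall quickly and then settle. A straight line cannot settle, and a quadratic that bends enough to follow an early fall must later rise.

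Objective 2 is trajectory variability and effect sizes for its predictors. The hypothesis in Context of this IRB application is about whether pain resolves or becomes chronic, which is an effect on the late level. If the curve is misshapen, a predictor that changes only the late level can show up partly as a day-of-surgery effect. That misallocated coefficient is what the later study would be designed on.

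**Working it through.** The documents give no expected trajectory, so there is no plan figure to reproduce. What follows is a conditional calculation.

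**Schedule (At Home Diary Assessments, Table 1).** Twice daily on days 4-14 gives 11 × 2 = 22; daily on days 15-28 gives 14; weekly on days 29-85 gives 9; monthly gives 3, assumed at days 112, 140 and 168. The total is 48, of which 36 fall by day 28 and 3 after day 85. Early data dominate the fit.

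**Assumed truth.** y(t) = 100·[p + (1 − p)·2^(−t/h)], with half-life h in days and plateau fraction p = 0, 0.2 or 0.3. Units are points per 100 at surgery, not MPQ-SF units. Each form is fitted by least squares to the 48 occasions, without noise or drop-out.

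**One case in full (h = 14, p = 0).** The fitted quadratic is 75.12 − 1.6932t + 0.007969t².
- Day 0: 75.1, against a true 100.
- Low point: 1.6932 / (2 × 0.007969) = day 106, at a value of −14.8.
- Day 168: 75.12 − 284.46 + 224.92 = 15.6, against a true 0.0.

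**Range over p = 0 to 0.3.**

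| Quantity | h = 7-28 | h = 42 | h = 60-90 |
|---|---|---|---|
| Quadratic, day-0 value (true 100) | 49-94 | 96-97 | 98-100 |
| Quadratic, day 168 too high by | 5.6-17 | 2.9-4.2 | about 2 or less |
| Quadratic, largest error, days 4-168 | 5.6-24 | 2.9-4.2 | about 2 or less |
| Straight line, largest error | 23-38 | 18-25 | 7-18 |
| Piecewise line (knots 14, 28, 85), largest error | at most 4.5 | at most 3.2 | at most 2.3 |

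At h = 7-28 the quadratic reaches its low point between days 98 and 124 and then rises by 8.5-34. Its noiseless R-squared is 0.72 at h = 7, 0.91 at h = 14 and 0.98 at h = 28. At h = 28 the fit looks good while day 168 is still 5.6-8.0 too high.

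**Day-0 slope.** At h = 7-28 the quadratic's linear term is 13-62% of the true day-0 slope. The piecewise first slope is 42-79%. Neither should be read as a day-0 quantity.

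**Predictors.** Take a factor that raises only the plateau, by 10: its true effect is 10·(1 − 2^(−t/h)), which is zero at day 0.

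| | h = 7 | h = 14 | h = 28 |
|---|---|---|---|
| True day-168 effect | 10.0 | 10.0 | 9.8 |
| Quadratic with intercept effect: day 0 (true 0) | 5.1 | 2.5 | 0.8 |
| Quadratic with intercept effect: day 168 | 8.3 | 8.4 | 9.0 |
| Quadratic, effect on time terms only: day 168 | 3.2 | 6.0 | 8.2 |
| Piecewise with intercept effect: day 168 | 10.0 | 9.9 | 9.9 |

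The time-terms-only row uses generalised least squares with a random intercept, and barely moves with the variance inputs.

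**Would a fit criterion discriminate?** In 360 simulated trials (75 patients, 19 lost to follow-up, residual SD 10 or 20), BIC preferred the quadratic to the line every time. With the piecewise and log(day) forms added, the quadratic was chosen in 0 of 160 trials at h = 7-28, 10 of 40 at h = 42, 28 of 40 at h = 60 and 40 of 40 at h = 90. In the remaining 80 trials, with two-phase exponential curves, log(day) was chosen in 78.

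**Other shapes.** Over 13 non-exponential curves the largest error was 0-14.6 for the piecewise line and 8.3-30 for the quadratic. The quadratic was better in one (12.2 against 13.7).

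**The case against.** **The plan already checks fit.** It does, and it moves to predictors only once a suitable first-level model is found, so the list of forms is not closed. A check could well flag the worst cases. But no criterion is stated, and the one change named is to a line, which fits worse than the quadratic throughout the table.

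**The curves are assumed.** This stands, and it limits the claim. The Background treats pain beyond two months as abnormal, which leans towards faster recovery, but that is a definition and not a measured curve.

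**Time zero is a small matter.** Largely correct. Moving the origin of a quadratic re-labels its coefficients and leaves the curve unchanged: at day 4 it is still 3.4-23.8 too low for h = 7-28. Earlier diaries help little. On a second assumed curve, 7 at surgery falling to 1, starting at day 1 instead of day 4 moves the intercept only from 3.9 to 4.5 (h = 7), 5.5 to 5.8 (h = 14) and 6.2 to 6.4 (h = 21). Shape is the main driver.

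**The predictor wording may not exclude the intercept.** A reader might infer that predictors act only on the time terms, and so quote the 3.2 / 6.0 / 8.2 row. The same paragraph makes variation in the intercept one of the triggers for the second-level model, so that reading is possible but not established.

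**Any curved form would do.** It would not. log(day) never levels off: with zero plateau and h = 7-14 it puts day 168 at −18 to −21, against a true value near 0.

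**Conclusion.** The point holds as a cheap improvement to a descriptive pilot. That day 0 has no scheduled MPQ-SF, and that neither named form can level off, follows from the documents and from algebra. The size rests on an assumed exponential fall with complete data: material at half-lives of 7-28 days, about 3-4 points at 42, and about 2 or less at 60-90.

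Three stronger readings are not supported:
- **That the pilot's conclusions fail.** The plan is primarily descriptive, no test or decision depends on these coefficients here, and the observed day 86-168 scores remain available.
- **That the quadratic will overstate late pain.** With 25% drop-out (19 of 75 lost after day 28, 56 or 85) its day-168 error ran from −18.6 to +36 at h = 7-28, depending on the random-effects structure, so the sign is not stable. The piecewise range was −7.4 to +2.4.
- **That day-0 quantities are unrecoverable by any model.** A correctly specified exponential would recover them from noiseless data. The caution applies to the linear, quadratic and piecewise fits.

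**What to change.** (a) **Shape.** Pre-name a piecewise-linear first-level form, with knots near days 14, 28 and 85, beside the quadratic and linear forms. Choose by a stated criterion such as BIC, and show the main coefficients under each form. log(day) may be listed as a further candidate with its limit stated, but not as the form that levels off.

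(b) **Time zero.** Reconcile At Home Diary Assessments with Outcome Measure(s) on whether an inpatient MPQ-SF is collected. If the schedule stands, set time zero at the first home MPQ-SF, use the Visit 1 MPQ-SF as a second-level covariate, and summarise the inpatient ratings separately. Do not interpret day-0 values or slopes from the linear, quadratic or piecewise fits. This step defines the intercept; it does not repair the curve.

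(c) **Predictors.** State that second-level predictors act on the intercept as well as the time terms. Report model-estimated pain at day 168 beside the observed day 86-168 scores.

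**Cost.** Plan wording and a few extra fits, with no new data. The piecewise form has five fixed time parameters, including the intercept, instead of three. A random late slope may not be estimable from about three calls per patient. Knots at diary changes are administrative and can miss the true bend. Choosing the form from the data makes standard errors somewhat optimistic, which is why coefficients should be shown under every form.

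### When the quadratic term is kept, the linear coefficient is the rate of change on the day of surgery, not change over time, and no overall-recovery contrast is planned beside it

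*Combined protocol and SAP*

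**What the plan says.** The Analytical Plan states that "the trajectories will be modeled using an intercept, slope, and quadratic term". The first-level model is "a model that consisted of only intercept (starting value), time, and time-squared as first-level predictors", and the intercept is set at the day of surgery, so time zero is surgery.

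The coefficients are described in turn. Of the linear one: "The slope estimates the linear change over time and represents the increase or decrease in the variable". Of the quadratic one: "the quadratic term estimates the acceleration or deceleration over time and reflects changes in the rate of change in pain reporting". The first description carries no statement that it applies at day 0 only.

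The model is to be checked and "will be reduced to a linear change model if conditions indicate". If participants vary enough, a second level relates the questionnaires and baseline sensory testing to both the linear and the quadratic components. The plan adds that "the model coefficients and their standard errors will be of primary interest to inform out later, definitive study".

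No mean rate of change, change to the end of follow-up, or predicted pain at a set day is named as a summary. The covariance of the coefficients is not mentioned.

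**The concern.** In a curve with a squared term, the linear coefficient describes the steepness at whichever day is coded zero. Here that is the day of surgery. A reader who takes the plan's description at face value would treat a predictor's effect on this coefficient as its effect on recovery over the whole follow-up, and the two can disagree.

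This bears on the second objective, which asks for effect sizes of factors that predict the pain trajectory, and on the stated use of the pilot as the basis for sizing a later study. The Background treats pain lasting beyond 2 months, and more clearly beyond 6 months, as the abnormal outcome. A rate on the day of surgery says little about that without the quadratic term, and the precision of any combined effect needs the covariance of the two coefficients.

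**Working it through.** The plan states no figure on this point, so there is none to reproduce. The check is algebra followed by illustrations.

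**Inputs from the documents.** Model form and time origin: Analytical Plan. Follow-up to day 168 and the diary schedule: At Home Diary Assessments and Table 1. N = 75: Sample Size.

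**Inputs assumed.** The documents give no pain values, recovery shape or variance components. All magnitudes below are illustrative.

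**1. What the linear coefficient is.** Let pain(t) = a + bt + ct², with t in days from surgery.
- Rate at day t: b + 2ct. At t = 0 this is b.
- Mean rate over days 0 to 168: (168b + 168²c)/168 = b + 168c. This is also the rate at day 84.
- The two agree only if c = 0.

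**2. How far apart they can be.** If the curve turns at day V, then c = −b/(2V), and the mean rate is b(1 − 84/V).

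| Assumed turning point | 1 − 84/V | Day-0 slope ÷ mean slope |
|---|---|---|
| day 250 | 0.664 | 1.5 |
| day 168 | 0.500 | 2.0 |
| day 120 | 0.300 | 3.3 |

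**3. A predictor can move the slope and not the end point.** Take time in 28-day units, so day 168 is 6 units. Assume predictor effects of +0.6 (linear) and −0.1 (quadratic), with none on the intercept.
- Effect on pain at day 168: 0.6 × 6 − 0.1 × 36 = 3.6 − 3.6 = 0.
- Effect on mean rate: 0.6 − 0.1 × 6 = 0.

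**4. Direction can reverse.** Compare two assumed groups, per day:
- b = −0.060, c = 0.00018: change by day 168 is −10.08 + 5.08 = −5.0 points.
- b = −0.050, c = 0.00010: change by day 168 is −8.40 + 2.82 = −5.6 points.

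The group with the steeper linear coefficient falls less.

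**5. Only the reading depends on coding.** An assumed exponential recovery (5-point fall, time constant 30 days) was fitted by a quadratic on an approximate version of the schedule. With time centred at days 0, 28, 84 and 168, the linear coefficient is −0.082, −0.062, −0.022 and +0.038 per day. The quadratic coefficient (0.00036) and the fitted day-168 score (2.58) are the same each time.

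**6. Precision of the mean-rate effect.** For a predictor's effects on b and c:

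Var(b + 168c) = Var(b) + 168² Var(c) + 336 Cov(b, c).

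The two standard errors supply the first two terms only. To size the third:
- The schedule was taken as 22 twice-daily entries (days 4 to 14), 14 daily, 8 weekly and 3 monthly, 47 in all.
- The covariance of the second-level coefficients was taken as proportional to D + s²(Z′Z)⁻¹. Here D is the between-patient covariance, s the residual SD and Z the schedule's design matrix. The factor for N = 75 cancels in the ratio.
- Assumed ranges: residual SD 2 to 4; slope SD 0.9 to 1.5 and quadratic SD 0.05 to 0.2 per 28-day unit; slope–quadratic correlation 0 to −0.9.

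Across these ranges the correlation between the two predictor effects runs from about −0.24 to −0.93. A standard error built without the covariance is about 1.15 to 3.7 times too large. With an assumed slope–quadratic correlation of zero, the ratio is about 1.15 to 2.2. Ratios above about 2.6 need an assumed correlation stronger than −0.5.

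**The case against.** The strongest reply is that the sentence should be read with its neighbours. The plan describes the quadratic term as a changing rate, examines predictors of both components, and carries forward all the coefficients. Nowhere does it call the slope an average or use it alone to measure recovery. The fitted curve is the same under any centring, and if the model is reduced to linear the description is right. The investigators will hold the fitted model, so the covariance is available to them. The pilot is declared mainly descriptive and sets no decision rule on the slope.

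All of this stands, and it limits the point to interpretation and reported output. A reader might infer that the analysis is wrong, or that the slope effects handed on will misstate recovery. The documents do not support that: it would happen only if the slope effect were read without the quadratic effect, and the plan does not say to do so.

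What the reply does not remove is that the description is incorrect for the model the plan starts from, and that no summary of overall recovery, with its own standard error, is promised.

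**Conclusion.** The point holds in a limited form. Whenever the quadratic term is kept, the linear coefficient is the rate on the day of surgery, and the plan's description of it is inaccurate. This follows from the stated model and needs no assumption. So does the fact that two separate standard errors do not give the precision of a combined effect.

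The sizes rest on assumptions: 1.5 to 3.3 for day-0 slope over mean slope depends on turning points at days 250 to 120, and about 1.15 to 3.7 for the standard error depends on variance components that the documents do not give.

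Two further inferences should be resisted.
- On this schedule, one patient's estimated linear and quadratic coefficients correlate at about −0.95. That is not the correlation between predictor effects, which also depends on between-patient variation.
- A reader might conclude that the later power calculation will rest on the wrong quantity or an inflated standard error. The documents do not describe that calculation, and nothing in them says that standard errors will be combined as if the covariance were zero.

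Severity is minor to moderate for a descriptive pilot.

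**What to change.** In the Analytical Plan:

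1. Replace the description of the slope with: when the quadratic term is kept, the linear term is the rate of change at surgery; if the model is reduced to linear, it is the constant rate of change.
2. Keep the planned coefficients and standard errors. For each predictor, also report two contrasts with standard errors from the full coefficient covariance matrix:
   - the effect on mean rate of change over days 0 to 168 (b + 168c);
   - the effect on predicted pain at day 168 (168b + 168²c, plus the intercept effect if the predictor enters there).

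These contrasts would then be available for the later power analysis. Which quantity that study is powered on is for its own protocol to decide.

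The cost is about two sentences and one contrast statement, with no new data and no change to the model. Day-of-surgery coding can stay. If time were centred at day 84 instead, the linear term would be the mean rate directly, but the intercept would become the day-84 level and the starting level would have to be reported as a contrast.

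### The second-level model is described as acting on the linear and quadratic terms only; if the intercept is really left out, a predictor's link to starting pain leaks into its change coefficients

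*Combined protocol and SAP*

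**What the plan says.** All of this is in the Analytical Plan of the combined protocol and SAP unless noted.

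- First level: "the trajectories will be modeled using an intercept, slope, and quadratic term". On the meaning of the first term: "The intercept is coded to represent the baseline level of the pain score (day of surgery").
- The first-level model is then glossed as change: "This first level model describes individual trajectories (change) across time". It "will be reduced to a linear change model if conditions indicate".
- Trigger for the second level: "if there is significant variation across participants in either the intercept or change parameters, a second level model will be specified".
- Targets of the second-level predictors: the "impact of the questionnaires and baseline sensory testing on the trajectories (i.e., linear and quadratic components of the first level model").
- Use of the results: "the model coefficients and their standard errors will be of primary interest", to inform the later study. Objective 2 likewise asks for effect sizes of factors that predict the pain trajectory.

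No sentence expressly places a predictor on the intercept or adjusts for starting level. None expressly keeps predictors out of it.

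On timing, the Pre-surgical Intervention section says: "After completion of baseline questionnaires (MPQ-SF, DSI, CATS) the Brief CBT Intervention will be viewed by the subject". The MPQ-SF is therefore a pre-surgical questionnaire, and Outcome Measure(s) names the same instrument as the primary outcome.

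**The concern.** The parenthesis defines the trajectories by two of the three terms from which the plan builds them. It also sits badly with the trigger: variation in the intercept alone can call for a second-level model whose stated targets leave the intercept out. Two analysts could fit different models from this text.

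The difference matters because omitting a predictor from the intercept equation is a constraint. It sets the predictor's effect on day-of-surgery pain to zero. If that effect is not zero, the predictor-by-time terms absorb part of it, and a predictor of level is reported partly as a predictor of recovery rate. Those change coefficients are what the pilot passes to the definitive study.

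**Working it through.** The plan gives no figure on this point, so there is none to reproduce. The check asks how large the leak would be under the literal reading.

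**Inputs from the documents.** N = 75 (Sample Size). Diary schedule (At Home Diary Assessments and Table 1): twice daily on days 4-14, daily on days 15-28, weekly to day 85, monthly to day 168.

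**Assumed, because the documents give no values.**
- Entries: 22 (days 4-14, half a day apart) + 14 (days 15-28) + 8 (days 29, 36, ..., 78) + 3 (days 112, 140, 168) = 47. Time t is in units of 100 days.
- Intercept variance 1, slope variance 0.3, no random quadratic term, residual variance 1.
- Intercept-slope correlation -0.5, 0 or +0.5.
- True effect on change zero. Effect on starting pain 0.5 per SD of the predictor, which is 0.25/1.25 = 20% of total intercept variance, r about 0.45.

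**Formula.** With V = ZDZ' + σ²I, Z = [1, t] and T = [t] or [t, t²], generalised least squares without the intercept term has bias (T'V⁻¹T)⁻¹T'V⁻¹1 × shift.

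**Linear model, by hand.** Here the formula reduces to bias = -(W01/W00) × shift, with W = D + σ²(Z'Z)⁻¹.
- Σt = 13.525, Σt² = 9.413, determinant = 47 × 9.413 - 13.525² = 259.5.
- σ²(Z'Z)⁻¹ has elements 9.413/259.5 = 0.0363, -13.525/259.5 = -0.0521 and 47/259.5 = 0.1811.
- W00 = 1.0363. W01 = ρ√0.3 - 0.0521 = -0.3260 / -0.0521 / +0.2217.
- Bias = 0.5 × 0.3260/1.0363 = 0.157; 0.5 × 0.0521/1.0363 = 0.025; -0.5 × 0.2217/1.0363 = -0.107.
- SE at ρ = -0.5: without the intercept term √[(0.4811 - 0.3260²/1.0363)/75] = 0.071; with it √(0.4811/75) = 0.080, a rise of 13%.

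**Results, same assumptions (bias, with SE in brackets).**

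| Coefficient | ρ = -0.5 | ρ = 0 | ρ = +0.5 |
|---|---|---|---|
| Linear model, slope | 0.157 (0.071) | 0.025 (0.080) | -0.107 (0.076) |
| Quadratic model, linear | 0.269 (0.158) | 0.142 (0.167) | 0.014 (0.171) |
| Quadratic model, quadratic | -0.082 (0.103) | -0.082 (0.103) | -0.082 (0.103) |

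**Sensitivity.**
- Shift 0.2 SD (r about 0.20): 0.2/0.5 = 40% of each value, all below one SE. Shift zero: no bias.
- Residual variance 2, ρ = 0: linear 0.265 (SE 0.224), quadratic -0.153 (SE 0.144). Both exceed one SE with no intercept-slope correlation.
- Slope variance 0.1-0.6 and residual variance 0.5-2, all three correlations: linear-model slope 0.23 to -0.18; quadratic-model linear coefficient 0.43 to -0.11, quadratic -0.04 to -0.15.
- Monthly calls on days 86, 114 and 142: linear 0.30 / 0.17 / 0.05, quadratic -0.12.
- 25% drop-out unrelated to pain (leaving day uniform on days 4-168): linear 0.28 / 0.15 / 0.03, quadratic -0.09, linear-model slope 0.16 / 0.03 / -0.10.

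**Simulation with estimated variances (REML, 300 runs, base schedule).** Without the intercept term, the quadratic model gives linear 0.231 / 0.118 / -0.008 and quadratic -0.058 to -0.065, somewhat smaller than the known-variance values. The linear model gives 0.169 / 0.028 / -0.099. With the intercept term, all these coefficients lie between -0.019 and 0.010.

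**Second simulation, linear model, other assumptions** (48 entries, intercept SD 2, slope SD 0.6 per 28 days, residual SD 1.5, effect on starting pain 1 point per SD, 200 runs per setting). At correlations -0.5 / -0.3 / 0 / +0.3, the nominal 5% test of a null slope effect rejects in 56% / 24.5% / 4.5% / 19.5% of runs without the intercept term. With it, rejection is 3% to 5.5%.

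**The case against.** The strongest reply is that the literal reading is the less coherent one. The plan seeks predictors of a trajectory that it builds from three terms, one of them the intercept. A second-level model that intercept variation can trigger, but that may not touch the intercept, would then have nothing to explain. The parenthesis can be read as naming the effects of interest rather than listing equations. This stands as far as intent goes. A reader might infer that the plan deliberately excludes the intercept and so commits the analysts to a biased model; the documents do not support that. They do leave the question open, and the only explicit list of targets omits the intercept.

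A second reply is that every magnitude is assumed. That stands too. A link between a predictor and starting pain is plausible for baseline MPQ-SF, but the documents do not show it, so it cannot be said that the pilot's estimates will be biased.

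A third is that the pilot is descriptive and is not intended to give definitive estimates. This carries less weight, because the coefficients and standard errors are the stated product.

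It is also tempting to say that the direction of the bias always follows the intercept-slope correlation, or that bias matters only when that correlation is not zero. Neither holds in the quadratic model: the quadratic coefficient is the same at all three correlations, and at residual variance 2 both coefficients exceed one SE at zero correlation.

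**Conclusion.** The point holds as a conditional one. The text on the second-level targets is inconsistent with the plan's own definition of the trajectory and with its trigger. Followed literally, it would bias the change coefficients of any predictor related to starting pain.

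Under the assumed values and a 0.5 SD shift, the bias reaches about 2.2 SE in the linear model (0.157/0.071, correlation -0.5) and 1.7 SE for the linear coefficient of the quadratic model (0.269/0.158). It is close to zero in other settings. In the linear model it depends mainly on the intercept-slope correlation; in the quadratic model residual variance matters as well. It is worth correcting before analysis. Confidence is medium, because intent is unclear and no size can be taken from the documents.

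**What to change.** Amend the second-level paragraph of the Analytical Plan to state that every second-level predictor enters the intercept equation as well as the linear and, if retained, the quadratic equation. Report level and change coefficients separately, each with its standard error. If this was already intended, correcting the parenthesis is enough.

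The cost is one sentence in the plan and one parameter per predictor. Under the assumptions above, the slope SE rises by at most about 8% in the quadratic model (0.158 to 0.171) and 13% in the linear model (0.071 to 0.080). With 25% drop-out the largest rises are about the same (0.166 to 0.179 and 0.077 to 0.086). No new data are needed.
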